2. RATIONALE, OBJECTIVES, AND BENEFIT - RISK ASSESSMENT

2.1 RATIONALE FOR PERFORMING THE TRIAL

This is the second trial with BI 1265162 and the first with multiple dose administration. The objective of this trial is to investigate the safety, tolerability and pharmacokinetics of BI 1265162 in healthy male subjects. The chosen population of healthy volunteers using multiple rising inhalative doses is adequate to provide the basis for the phase 2 clinical development program of BI 1265162 in CF and COPD. This trial will provide pharmacokinetic information in healthy volunteers at steady state exposure.

The inclusion of male healthy volunteers as a trial population in phase I studies is ideal as they provide relatively stable physiological, biochemical and hormonal conditions (steady state) for studying drug effects. Healthy volunteers can be tested under standardised conditions in an environment which allows repeated testing.

In this multiple rising dose (MRD) study, within each dose group, all actively treated individuals will receive the same BI 1265162 dose. The next higher dose will only be administered (to the next group) if the treatment in the preceding dose groups was safe and showed acceptable tolerability.

Dose Selection

It is intended to investigate the following dose levels of BI 1265162 in the MRD part of this trial: 10, 30, 100, 300 and 600µg twice daily (bid) for Days 2-7 and single dose on Day 1 and 8. The background for this dose selection is described in the following.

Starting dose

Considering the favourable preclinical and clinical safety profile of BI 1265162, and taking into consideration other systemic and inhaled ENaC inhibitors which have been well tolerated, with known, easily monitorable and reversible side effects (changes in electrolytes), a sub-therapeutic dose of 10 µg bid has been selected as the starting dose in this MRD trial. This dose is within the range of ED50 (cf. Table 2.1: 1).

Maximum dose and dose escalation

As stated above, a minimum daily dose of approximately may be required to achieve therapeutic exposure to BI 1265162.

Trial Protocol Page 26 of 84

Proprietary confidential information © 2018 Boehringer Ingelheim International GmbH or one or more of its affiliated companies

However, higher doses might still be well tolerated while providing a larger magnitude of therapeutic effects.

Further, even if the therapeutic dose turned out to be as low as higher than therapeutic doses are typically explored in MRD studies to provide a safety margin for following studies e.g. drug-drug-interaction studies, or patients with impaired excretion function, etc., where substantial increases in exposure may be observed. Studies in patients may demonstrate that an ED_{70} is insufficient to show a clinical effect and even higher doses of BI 1265162 are required e.g. in case an

(cf. Table 2.1: 1). To adequately address all these aspects a dose of $600~\mu g$ bid has been selected as the maximum dose. This dose will not exceed the highest (and well tolerated) tested dose in the SRD 1399.0001 of

The relevant findings in the toxicology studies in the rat were changes in serum and urine electrolytes due to the mode of action of an ENaC antagonist which will be fully reversible and will be monitored thoroughly in this clinical trial. In addition, effects on blood electrolytes should be demonstrable with increasing dosing, so an acute increase would not be expected. No such findings were seen in the SRD trial 1399.0001.

Boehringer Ingelheim BI Trial No.: 1399-0002 c15848749-03

04 Jul 2018

Page 27 of 84

Proprietary confidential information © 2018 Boehringer Ingelheim International GmbH or one or more of its affiliated companies

Table 2.1: 2 1399.0001 preliminary results Geometric Mean PK Parameter (gCV%) [* Median (Min-Max)]

Trial Protocol

A noncompartmental prediction of BI 1265162 plasma concentrations based on the preliminary PK results of study 1399.0001 revealed that BI 1265162 systemic exposure increases approximately dose-proportional over the studied dose range. Bid dosing results predicted in only relatively little accumulation. Steady-state is predicted to reach with respect to average, peak and trough concentrations by 4-5 days.

Preliminary results from the SRD 1399.0001 show that urinary excretion of BI 1265162 was around 1% of the administered dose within 48 hours after inhalation. Thus the risk of effects on the kidney regarding exchange of urine electrolytes is seen to be low.

Based on the above considerations a stepwise and careful dose increase up to a maximum dose of $600~\mu g$ bid has been selected for this trial. This selection is supported by the overall favourable preclinical and clinical safety profile of BI 1265162 in addition to the well

Proprietary confidential information © 2018 Boehringer Ingelheim International GmbH or one or more of its affiliated companies

documented effects of ENaC inhibition in man. Dose escalation will be in the range of factor 3 and the escalation factor will be lower than 2 for the higher dose range. This dose escalation scheme is considered to be adequate and safe, particularly when the good safety profile of BI 1265162 seen in the SRD 1399.0001 is taken into consideration.

2.2 TRIAL OBJECTIVES

The primary objective of this trial is to investigate the safety and tolerability of BI 1265162 in healthy male subjects following inhalative administration of multiple rising doses.

Secondary objectives is the exploration of the pharmacokinetics (PK) including dose proportionality and time dependency of BI 1265162 after multiple dosing

A description of the endpoints to be determined, and the observations along with specific information as how to collect the data for that information, is provided in Section 5.

2.3 BENEFIT - RISK ASSESSMENT

Participation in this study is without any (therapeutic) benefit for healthy subjects. Their participation in the study, however, is of major importance to the development of BI 1265162. The subjects are exposed to the risks of the study procedures and the risks related to the exposure to the trial medication.

Procedure-related risks

The use of an indwelling venous catheter for the purpose of blood sampling may be accompanied by mild bruising and also, in rare cases, by transient inflammation of the wall of the vein. In addition, in rare cases a nerve might be injured while inserting the venous catheter, potentially resulting in paresthesia, reduced sensibility, and/or pain for an indefinite period. The same risks apply to venipuncture for blood sampling.

The total volume of blood withdrawn during the entire study per subject will not exceed the volume of a normal blood donation (500 mL). No health-related risk to healthy subjects is expected from this blood withdrawal.

Drug-related risks and safety measures

As the nature of the target and the mechanism of action of BI 1265162 are well understood, comparable compounds have been tested internally and by other companies before, and the animal models are believed to be predictive for the effects in humans, BI 1265162 is not seen as a high risk compound. The specific mechanism of action is also well recognized for when administered systemically (orally) as a diuretic with a well-established safety profile and known side effects (effects on serum and urine electrolytes at exposures much higher than expected to be achieved with the current inhaled compound). Healthy subjects will not be exposed to undue risks and AEs in relation to the information expected from this trial.

The pharmacological effects of BI 1265162 are dose dependent and no evidence for prolonged or irreversible effects has been observed.

Trial Protocol

Page 29 of 84

Proprietary confidential information © 2018 Boehringer Ingelheim International GmbH or one or more of its affiliated companies

The following safety measures will be applied in this study in order to minimize the risk for healthy volunteers:

- Careful dose selection as described in Section 2.1.
- For safety reasons, each dose group of 10 subjects (8 on active drug, 2 on placebo) will be divided into 2 cohorts of 5 subjects each (4 on active drug, 1 on placebo). Both cohorts will be dosed in a randomized fashion and each drug administration will be separated by at least 10 minutes. For inhalative administered drugs, this is usually a sufficient time frame to observe acute effects.
- For each dose group, the 2 cohorts will be separated by at least 5 days (first dosing of the first cohort and first dosing of the second) to assess steady state conditions of the first cohort. A continuous safety evaluation, including results of safety laboratories, ECG readings, spirometry, recordings of vital signs and adverse events will be performed before the individual subject and the subsequent cohort is dosed.
- Based on the preclinical toxicology findings and taking the mode of action into consideration, dose escalation will be stopped as soon as at least 2 subjects at one dose level on active drug showed serum potassium levels > 5.5 mmol/L in non-hemolyzed blood.
- An extensive safety laboratory will be performed with special focus on serum electrolytes (see Flow Chart).
- Lung function assessments will be performed via spirometry.
- Only subjects with a normal kidney function (using the eGFR, calculated from serum creatinine using CKD-EPI formula) will be included in the study
- The subjects will stay at the trial site from 1 day prior first dosing till at least 48h after last study drug administration at each dose level.
- During in house-confinement the subjects will be under medical observation and thoroughly monitored for both expected and unexpected adverse events.
- Only if the respective dose of BI 1265162 is safe and showed acceptable tolerability and if the stopping criteria are not met (refer to Section 3.3.4.2), the next higher dose will be given at least 5 days later (referring to the last dosing of the 1st subject of each dose group).

Although rare, a potential for drug-induced liver injury (DILI) is under constant surveillance by sponsors and regulators. Therefore, this trial requires timely detection, evaluation, and follow-up of laboratory alterations in selected liver laboratory parameters to ensure subjects' safety, see also Section 5.2.2.1, adverse events of special interest.

In summary, BI 1265162 is in early clinical development. Single doses up to were well tolerated in the first in man trial 1399.0001. Based upon preclinical and early clinical data for BI 1265162 and clinical information from systemically and inhaled administered ENaC inhibitors and competitor inhaled compounds as well as the implemented safety measures described above, healthy subjects will not be exposed to undue risks. Healthy

Boehringer Ingelheim BI Trial No.: 1399-0002 c15848749-03

04 Jul 2018

Trial Protocol

Page 30 of 84

Proprietary confidential information © 2018 Boehringer Ingelheim International GmbH or one or more of its affiliated companies

volunteers are not expected to have any direct medical benefit from participation in this clinical trial with BI 1265162, as is the usual case in such phase I trials. Subjects will be closely monitored. BI 1265162 has the potential to be an inhalative treatment for CF, a disease of high unmet medical need. The expected potential benefits for patients and the important information expected from this trial as a basis for further clinical development of this compound are felt to outweigh the potential risks and justify exposure of healthy human volunteers in the clinical development of BI 1265162.

C15848749-03 Trial Protocol Page 31 of 84

Proprietary confidential information © 2018 Boehringer Ingelheim International GmbH or one or more of its affiliated companies

3. DESCRIPTION OF DESIGN AND TRIAL POPULATION

3.1 OVERALL TRIAL DESIGN AND PLAN

This multiple-rising dose trial is designed as double-blind, randomised, and placebocontrolled within parallel dose groups.

A total of 50 healthy male subjects is planned to participate in the trial, according to 5 sequential groups comprising 10 subjects per group. However, additional subjects may be entered to allow testing of additional doses on the basis of experience gained during the trial conduct, provided the planned and approved highest dose will not be exceeded. Thus, the actual number of subjects entered may exceed 50, but will not exceed 70 subjects entered. Such changes may be implemented via non-substantial CTP Amendments.

Within each dose group, 8 subjects will receive the active drug and 2 will receive placebo. Only one dose is tested within each dose group. Each dose group will consist of 2 cohorts (5 subjects each, 4 on active drug and 1 on placebo) which will be treated subsequently for safety reasons. The time interval between these cohorts will be at least 70 hours from first subject dosed.

The dose groups to be evaluated are outlined in Table 3.1: 1 below.

Table 3.1: 1 Dose groups

Dose Group	1	2	3	4	5	
Dose (µg) bid	10	30	100	300	600	
Number of subjects	10	10	10	10	10	
Subjects receiving placebo	2	2	2	2	2	
Subjects receiving active drug	8	8	8	8	8	

The dose groups will be investigated consecutively in ascending order of doses, maintaining a time interval of at least 5 days between the last drug administration in the previous dose group and the first drug administration of the subsequent dose group. The decision to proceed to the next dose group will be based upon the safety and tolerability of the preceding dose groups. The next dose will only be given if, in the opinion of the investigator, no safety concerns arose in the preceding dose group (i.e. no dose-limiting events occurred) and if none of the pre-specified trial-specific stopping criteria were met (refer to Section 3.3.4.2).

A documented Safety Review must take place prior to each dose escalation. Furthermore, an unscheduled safety review meeting can be requested anytime for any reasonable cause by the Principal Investigator (or an authorised deputy) or the sponsor of the study, e.g. because of any unforeseen adverse events, etc. Dose escalation will only be permitted if no safety concerns exist in the opinion of the Principal Investigator (or an authorised deputy) and the trial clinical monitor (or an authorised deputy).

Although no formal Safety Review meeting will take place within a given dose group, safety will be continuously monitored during this trial, and an individual will only be dosed in the

Page 32 of 84

Proprietary confidential information © 2018 Boehringer Ingelheim International GmbH or one or more of its affiliated companies

absence of any safety concern (i.e. no dose-limiting events occurred) and if none of the prespecified trial-specific stopping criteria have been met (refer to Section 3.3.4.2).

The minimum data set for review consists of the following data:

- AEs in the current and preceding dose groups (including clinically relevant findings from ancillary safety testing listed below) (Note: AEs may be ongoing at the time of Safety Reviews and AE information may be subject to change prior to Database Lock)
- Results from 12-lead EGG in the current and preceding dose groups.
- Vital signs in the current and preceding dose groups
- Spirometry data
- Clinical laboratory tests in the current and preceding dose groups
- Check of criteria for stopping subject treatment as per Section 3.3.4.1

The decision to escalate the dose will be made jointly by the Principal Investigator (or an authorised deputy) and the trial clinical monitor (or an authorised deputy) after in-depth analysis of all available safety data, especially SAEs (if occurred), AEs and out-of-range laboratory results (if considered clinically significant). Safety Reviews can be conducted face-to-face or by video/telephone conference. The trial clinical monitor is responsible for organization and minutes of the reviews. Minutes will be signed off by the Principal Investigator (or an authorised deputy) and filed in the ISF and TMF.

The investigator (after consultation with the sponsor) is allowed to alter the scheduled dose levels (e.g. add low and/or intermediate dose levels) on the basis of experience gained during the study, provided the planned and approved highest dose is not exceeded. In this case, the total number of subjects in this trial might increase. The investigator and/or the sponsor should stop dose escalation in case the safety evaluation leads to concerns that would not allow higher dosing.

An overview of all relevant trial activities is provided in the Flow Chart. For visit schedules and details of trial procedures at selected visits, refer to Sections 6.1 and 6.2, respectively.

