4.2.2.2 Restrictions on diet and life style

Prior to Day -1, Day 1, Day 5 and Day 8 the subjects have fasted for at least 8 h.

While admitted to the trial site the subjects are restricted from consuming any other foods or drinks than those provided by the staff. Standardized meals will be served at the time points described in the Flow Chart. Composition of food on Day -1, Day 1, Day 5 and Day 8 should be identical. Use of table salt is not allowed during in-house confinement at the trial site.

On Day -1, Day 1, Day 5 and Day 8, from 1 h before drug intake until lunch, fluid intake is restricted to 240 mL of water served at 2 h and 4 h post-dose (mandatory for all subjects). From lunch onwards, liquid intake is restricted to an additional 3000 mL. Subjects will be asked to drink the additional amount till one hour prior to the stop of urine collection on the following day. The total amount of liquid intake will be documented.

Grapefruits, Seville oranges (sour or bitter oranges) and their juices, and dietary supplements and products including St. John's wort (Hypericum perforatum) are not permitted starting 7 days before the first administration of trial medication until 24 h after last administration of trial medication.

Alcoholic beverages, consumption of seafood and dried fruits are not permitted from 48 hours before the study drug administration and until 24 h after last administration of trial medication.

Smoking is not allowed during in-house confinement at the trial site.

Methylxanthine-containing drinks or foods (such as coffee, tea, cola, energy drinks, and chocolate) are not during in-house phase.

Excessive physical activity (such as competitive sport) should be avoided starting 7 days before the first administration of trial medication until the end of study examination.

Direct exposure to the sun or exposure to solarium radiation should be avoided during the entire study

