Proprietary confidential information © 2018 Boehringer Ingelheim International GmbH or one or more of its affiliated companies

Table 5.2.3: 1 Routine laboratory tests (cont'd)

Category	Test name	\mathbf{A}^{1}	B^2	C^3
24h collection Urine	Urine potassium	-	X	-
	Urine sodium	-	X	-
	Urine chloride	-	X	-
	Urine creatinine	-	X	-
	Urine-aldosterone	-	X	-
Urinalysis (Stix)	Urine nitrite	X	X	X
[Urin-Sediment will be	Urine protein	X	X	X
performed, if urinalysis	Urine glucose	X	X	X
abnormal]	Urine ketone	X	X	X
	Urobilinogen	X	X	X
	Urine bilirubin	X	X	X
	Urine RBC	X	X	X
	Urine WBC	X	X	X
	Urine pH	X	X	X
Urine sediment	Only positive findings will be reported (for			
(microscopic	instance, the presence of sediment bacteria,			
examination if	casts in sediment, squamous epithelial cells,			
erythrocytes, leukocytes	erythrocytes, leukocytes)			
nitrite or protein are				
abnormal in urine)				

¹A: parameters to be determined at screening examination

The tests listed in Table 5.2.3: 2 are exclusionary laboratory tests which may be repeated as required. The results will not be entered in the CRF/database and will not be reported in the CTR. It is planned to perform these tests during screening only. Drug screening will be performed at screening and on Day 1.

²B: parameters to be determined during the study (for time points refer to Flow Chart)

³C: parameters to be determined during the Follow-up-examination

^{*} Urine collection fractions will be stored intermittent in a refrigerator. All collected fractions (0-24h) will be mixed for the 24h urine electrolyte measurement (intervals from 12:00-24:00, 108:00-120:00,180:00-192:00h will only be used for urine electrolytes not PK). Mixing should be done by transferring the entire content of all collection containers into a single PE/PP or glass container, and stirring the mixed fractions for about 1 min (manually or using a stir bar or other stirring device out of PE, PP, Teflon or glass).

c15848749-03 Page 52 of 84 Proprietary confidential information © 2018 Boehringer Ingelheim International GmbH or one or more of its affiliated companies

Table 5.2.3: 2 Exclusionary laboratory tests

Functional lab group	Test name		
Drug screening (urine)	Amphetamine/MDA		
2 rag servening (winter)	Barbiturates		
	Benzodiazepine		
	Cannabis		
	Cocaine		
	Methadone		
	Methamphetamines/MDMA/XTC		
	Opiates		
	Phencyclidine		
	Tricyclic antidepressants		

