6.7 BASELINE, TIME WINDOWS AND CALCULATED VISITS

There will be a centralised evaluation of 12-lead ECG recordings at the time points specified in [Table 6.7: 1](#).

Triple ECGs will be recorded at Visit 2 assessments and will be evaluated by a central lab. At Visit 1 and 3 only single ECGs will be recorded. This data will not be evaluated centrally. At predose (Visit 2, Day 1, planned time point -01:30, notation for data transfer -01:30, -01:25, and -01:20), three triplicate ECGs (9 single ECGs) will be recorded.

For all on-treatment assessments as well as for the 3 predose triplicates, only the first of the 3 replicate ECGs at a single assessment time will be evaluated centrally.

The baseline value of an ECG variable is defined as the mean of the first single ECG measurement of each triple ECG prior to first drug administration.

Table 6.7: 1 Time schedule of 12-lead ECG recordings with centralised evaluation

Visit	Day	Planned time [hh:mm] - relative to respective drug administration	Study phase
2	1	-01:30	Baseline
		00:10	On-treatment
		01:00	
		04:00	
		12:00	
	2	24:10	
	3	48:10	
	5	96:10	
	6	120:10	
	8	164:30	
		168:10	
		169:00	
		172:00	
		180:00	
	9	191:30	

For urine electrolytes there is a whole baseline day to have time matched baseline measurements (see [Table 6.7: 2](#) for details).

In all other analyses the last non-missing value determined prior to the first dosing of BI 1265162 will be defined as baseline.

Time windows are defined in Section 6.1 of the CTP. Adherence to time windows will be checked at the RPM/DBLM.

Unscheduled measurements of laboratory data, vital signs or spirometry data will be assumed to be repeat measurements of the most recent scheduled measurement (e.g. for follow-up or confirmation of a particular value). Therefore, unscheduled measurements will be assigned to the planned time point of the previous scheduled measurement.

Table 6.7: 2 Time schedule of urine electrolyte measurements

Visit	Day	Planned time interval [hh:mm] - relative to respective drug administration (planned time at the day)	Study phase
2	-1	-24:00 to -20:00 (08:00 to 12:00)	Baseline
		-20:00 to -16:00 (12:00 to 16:00)	
		-16:00 to -12:00 (16:00 to 20:00)	
		-12:00 to 00:00 (20:00 to 08:00 on Day 1)	
	5	96:00 to 100:00 (08:00 to 12:00)	On-treatment
		100:00 to 104:00 (12:00 to 16:00)	
		104:00 to 108:00 (16:00 to 20:00)	
		108:00 to 120:00 (20:00 to 08:00 on Day 6)	
	8	168:00 to 172:00 (08:00 to 12:00)	
		172:00 to 176:00 (12:00 to 16:00)	

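### Protocol Section 3.1 sets a 70-hour minimum between the two cohorts of a dose group, too short for the steady-state check for which Section 2.3 sets 5 days

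*Protocol*

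**What the plan says.** Three parts of the protocol bear on this interval.

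- **Section 3.1**, which describes the design, splits each dose group into two cohorts treated one after the other for safety reasons, and then says: "The time interval between these cohorts will be at least 70 hours from first subject dosed".
- **Section 2.3** lists the measures that will be applied to limit risk to volunteers. One is that "the 2 cohorts will be separated by at least 5 days (first dosing of the first cohort and first dosing of the second" cohort). The stated purpose is "to assess steady state conditions of the first cohort". The same item calls for a continuous safety evaluation covering laboratory results and ECG, and adds that "spirometry, recordings of vital signs and adverse events will be performed before the individual subject and the subsequent cohort is dosed".
- **Section 2.1** gives the kinetic prediction: "Steady-state is predicted to reach with respect to average, peak and trough concentrations by 4-5 days".

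Section 3.1 also says that no formal Safety Review meeting is held within a dose group. A documented review is required only before escalation to the next dose. The two global amendments change the upper age limit and one planned time on Day 3. Neither they nor the SAP deals with the cohort interval.

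**The concern.** Both figures run from first dosing, so they describe the same interval, and a difference in definition does not explain the 50 h between them. Only the 5-day figure comes with a reason, and that reason depends on cohort 1 having reached steady state.

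This is the first multiple-dose trial of the drug. Section 1.2.5 reports serum potassium increases after multiple dosing with other inhaled drugs of the class, and Section 2.1 says an acute electrolyte increase is not expected. The effect to watch for is therefore one that repeated dosing would bring out. Because no formal review falls between the cohorts, the interval determines how much repeated-dose information from cohort 1 exists when cohort 2 begins. A reader who takes the gap from the design section would start cohort 2 before the condition named in Section 2.3 could be assessed.

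**Working it through.** The protocol gives no derivation of the 70 h, so there is no figure to reproduce. The check is a timeline in hours from the first subject's first dose.

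**Inputs**

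- Dosing (Protocol 4.1.4 and Flow Chart): single dose at 0 h; twice daily on Days 2-7, at 24, 36, ..., 156 h; single dose at 168 h. Total 1 + 12 + 1 = 14 doses.
- Candidate gaps: 70 h (Section 3.1) and 5 × 24 = 120 h (Section 2.3).
- Predicted time to steady state (Section 2.1): 4-5 days, or 96-120 h. The start point is not stated, so both are tried.
- Assessment times: Protocol Flow Chart; SAP Table 6.7: 1 (ECG) and Table 6.7: 2 (urine electrolytes).

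**Step 1. Exposure reached**

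- Before 70 h: doses at 0, 24, 36, 48 and 60 h, so 5 of 14; twice-daily dosing for 70 − 24 = 46 h.
- Before 120 h: those plus 72, 84, 96 and 108 h, so 9 of 14; twice-daily dosing for 120 − 24 = 96 h.

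**Step 2. Shortfall against predicted steady state**

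| Start point of the 4-5 days | Steady state at | 70 h gap short by | 120 h gap short by |
|---|---|---|---|
| First dose (0 h) | 96-120 h | 26-50 h | 0 h |
| Start of twice-daily dosing (24 h) | 120-144 h | 50-74 h | 0-24 h |

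The 70 h gap falls short on either start point. The 120 h gap is sufficient on the first and reaches the lower end of the range on the second.

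**Step 3. Cohort 1 data under twice-daily dosing (after 24:00)**

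| Assessment | By 70 h | By 120 h |
|---|---|---|
| Serum electrolytes | 1 (50:00) | 2 (adds 74:00) |
| ECG and vital signs | 2 (24:10, 48:10) | 3 (adds Day 5) |
| Spirometry | 0 | 1 (Day 5) |
| Urine electrolyte fractions closed | 0 | 3 by 108:00; the fourth closes at 120:00 |

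The last urine interval in SAP Table 6.7: 2 is "108:00 to 120:00 (20:00 to 08:00 on Day 6"), so it closes exactly when a 120 h gap ends. The next serum electrolyte sample after 74:00 is at 122:00, 2 h after a 120 h gap has ended.

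The Day 5 block of the Flow Chart is damaged in the available text. The Day 5 spirometry is taken from the row printed at 100:00. The Day 5 ECG is confirmed by SAP Table 6.7: 1, at 96:10. The 70 h counts and the urine counts do not depend on that block.

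**Step 4. Time cost of the longer gap**

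120 − 70 = 50 h per dose group; 50 × 5 = 250 h = 10.4 days for the five planned groups. If the 70-subject ceiling were used for 70 / 10 = 7 groups, 50 × 7 = 350 h = 14.6 days.

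**The case against.** The strongest reply is that 5 days is already the rule. Section 2.3 presents its list as measures that will be applied, and both figures are minima. Waiting 5 days satisfies both sections, while 70 h breaches Section 2.3. Section 3.1 never claims that 70 h is for assessing steady state. The trial has one centre, so there is little room for sites to diverge. On this view, one number in Section 3.1 is out of step and nothing more. The reply is right about the consequence: a reader might infer that the protocol as a whole allows cohort 2 to start at 70 h, and it does not. But the design section still states a minimum that would defeat a listed safety measure, and nothing says which section prevails. If 70 h was the intended figure, then Section 2.3 misdescribes the measure. One of the two sections has to change.

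Other limits also stand. Cohort 1 is not unobserved at 70 h. It also has electrolytes at 2:00, the Day 2 safety laboratory at 23:55, spirometry at 0:20 and 2:00, and four post-dose ECG and vital-sign sets from Day 1, and Section 2.3 does not restrict its evaluation to data under twice-daily dosing. Both cohorts receive the same dose, and no one is dosed if there is a safety concern or a stopping criterion has been met. Section 2.1 predicts relatively little accumulation and reports no electrolyte findings in the single-dose trial, whose top dose is not exceeded here.

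Two stronger readings of what 5 days would bring are not supported.

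- A reader might infer from the diet rule ("Composition of food on Day -1, Day 1, Day 5 and Day 8 should be identical") that Day 5 is a full profile day. That rule concerns meals. As far as the damaged block can be read, Day 5 has one pre-dose and one early post-dose plasma sample; the full plasma profiles are on Days 1 and 8.
- A reader might infer that a 120 h gap delivers the complete Day 5 electrolyte picture. It gains no potassium value between 96 and 120 h, although potassium is the analyte in the stopping rule. Section 5.2.3 adds that "All collected fractions (0-24h) will be mixed for the 24h urine electrolyte measurement", so a pooled Day 5 urine result cannot be in hand at 120 h.

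**Conclusion.** Section 3.1 is wrong as written and should be corrected. Its figure is 50 h below the one in Section 2.3 and does not reach predicted steady state on either start point. This rests on the sponsor's own prediction of 4-5 days, which cannot be checked because the half-life is not visible in the available text.

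The practical effect is modest: a small amount of extra repeated-dose data on cohort 1, in a setting where other safeguards apply and where compliance with both sections already means 5 days. The finding does not show that any subject would be dosed unsafely. Nor does it show that 5 days is ample, since counted from the start of twice-daily dosing 5 days may itself be up to 24 h short.

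**What to change.** In Protocol Section 3.1, replace the 70-hour clause with a minimum of 5 days, counted from the first dosing of the first cohort to the first dosing of the second, so that it matches Section 2.3. Section 2.3 needs no change on this point.

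This is a wording amendment and adds no subjects, procedures or samples. The time cost is at most the 50 h per dose group worked out above, and arises only if the site would otherwise have used 70 h.
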